5.7.1.6 Overall Neuropathy Limitation Scale (ONLS)

The Overall Neuropathy Limitations Scale (ONLS), was derived by modifying the Overall Disability Sum Score (ODSS) slightly.

The ODSS focuses on upper and lower limb functions, and consists of a checklist for interviewing patients. It is scored from 0 to 5 on the upper limb section and from 0 to 7 on the lower limb section. A score of 0 indicates no limitations (the ceiling of the scale) and a score of 5 or 7 indicates no purposeful movement.

To reduce a possible ceiling effect, Graham et al. have modified the ODSS to include climbing stairs and running. Specifically, the ODSS item “Does the patient have difficulty walking?” has been supplemented with “Does the patient have difficulty running or climbing stairs?” on the new measure, the Overall Neuropathy Limitations Scale. Therefore, to score 0 (indicating no limitations) on the lower limb section of the ONLS, the patient must now have no difficulty running or climbing stairs, in addition to walking. The remaining scoring criteria are not different from those in the ODSS.

The simplicity of the ODSS is shared by the ONLS, but the ONLS has better content validity and less ceiling effect, which may make it more useful for clinical practice and research (Graham 2006).

The reliability of this scale is substantial in CMT patients (Solari 2007).

The ONLS is displayed in appendix, and will be recorded in the CRF at each visit.

5.7.1.7 Timed 10-meter walk test

In this test the patient is instructed to walk at a comfortable, normal pace for 10 meters. Only the middle 6 m, however, is timed to eliminate the effects of acceleration and deceleration. Start and stop of performance time coincides with the toes of the leading foot crossing the 2-m mark and the 8-m mark, respectively. From these data, the speed may be calculated by dividing the middle 6 m by the time (in seconds) required to walk the 6 m (Wolf 1999).

The reliability of this test is excellent for CMT patients (Solari 2007).

A full instruction for the realisation of the test is displayed in appendix. The test will be performed and result recorded in the CRF at each visit.

5.7.1.8 6-min walk test

The 6MWT is a practical simple test that requires a 30 m (100-ft) hallway but no exercise equipment or advanced training for technicians. This test measures the distance that a patient can quickly walk on a flat, hard surface in a period of 6 minutes. The patient is allowed to self-pace and is encouraged every two minutes by the examiner as he traverses back and forth along a marked walkway.

The reliability and validity of this test has been investigated extensively as it has been used as a functional outcome measure for adults with cardiopulmonary dysfunction. (American Thoracic Society statement: guidelines for the 6MWT, 2002). It has also been used as a functional outcome measure for individuals with multiple sclerosis (Goldman et Al 2008).

The test is more extensively described in appendix and will be performed and recorded in the CRF at each visit.

5.8 Safety evaluations

At each visit, the presence of all serious Adverse Drug Reactions (ADR) will be notified into the CRF and immediately reported to sponsor in the SAE form. SAE/ADR will immediately be reported to the Pharmacovigilance Unit of the sponsor.

5.8.1 Rating table of adverse events

Safety will be evaluated by vital signs, physical examination (including neurological examination), and biological signs. The following safety endpoints will be checked and recorded in the CRF:

- Adverse events presence,
- Vital signs including heart rate, blood pressure and weight.
- Clinical examination abnormalities,
- Standard laboratory testing abnormalities.

5.8.2 Safety endpoints

Standard clinical and adverse event monitoring will be done at each visit.

Standard laboratory testing (plasma biochemistry and haematology) will be done at W0 and W48 and consists in measurement of:

- Safety panel: RBC, hemoglobin, mean corpuscular volume, WBC, platelets, electrolytes (Na, K, Cl, HCO₃), protein, creatinine, glomerular filtration rate, fasting blood glucose, AST, ALT, total and free bilirubin, gamma glutamyl transferase, alkaline phosphatase, triglyceride, cholesterol, PT, aPTT, INR

6 ADVERSE EVENTS

6.1 Definitions

Adverse Event (AE):

Any untoward medical occurrence in a patient administered a pharmaceutical product and which does not necessarily have a causal relationship with this treatment.

An adverse event can therefore be any unfavourable and unintended sign (including an abnormal laboratory finding, for example), symptom or disease temporally associated with the use of a medicinal (investigational) product, whether or not considered related to the medicinal (investigational) product.

Examples of AEs include, but are not limited to, the following:

- Abnormal test findings (see definition below)
- Clinically significant symptoms and signs
- Hypersensitivity
- Progression/worsening of underlying disease,
- Drug abuse
- Drug dependency
- Protocol-related adverse event (see definition below)
- Additionally, they may include the signs or symptoms resulting from
 - Drug overdose

- Drug withdrawal
- Drug misuse
- Drug interactions
- Exposure during pregnancy
- Exposure via breastfeeding
- Medication error

A protocol-related adverse event is an AE occurring during a clinical study that is not related to the investigational product, but is considered to be related to the research conditions, i.e., related to the fact that a patient is participating in the study.

Serious Adverse Event (SAE):

A serious adverse event (SAE) is any untoward medical occurrence that, at any dose:

- Results in death
- Is life-threatening, (Note: The term “life-threatening” in the definition of “serious” refers to an event in which the patient was at risk of death at the time of the event. It does not refer to an event, which hypothetically might have caused death if more severe.)
- Requires hospitalization or prolongation of existing hospitalization
- Results in disability/incapacity
- Is a congenital anomaly/birth defect.

Medical or scientific judgment should be exercised in deciding whether reporting is appropriate in other situations, such as important medical events that may not be immediately life threatening or result in death or hospitalization but may jeopardize the patient or may require medical or surgical intervention to prevent one of other outcomes listed in the above definition. These should also be considered serious.

Important:

All AE/SAE occurring in the study associated or not to the study drug shall be notified to the Sponsor Pharmacovigilance Unit.

Suspected Unexpected Serious Adverse Reaction (SUSAR) suspected to be related to an interaction between an IMP and a NIMP should be reported.

Medication Errors:

In this protocol, a reportable medication error includes the following:

- The administration of an unassigned treatment.
- An investigational medicinal product temperature excursion not approved by the Sponsor’s clinical pharmacy or designee.
- Inadvertent or accidental exposure to an investigational product with or without an AE.

Whether or not the medication error is accompanied by an AE, as determined by the investigator, the medication error and, if applicable, any associated adverse event(s) is captured on an adverse event (AE) on the CRF (refer to Adverse Event Reporting section for further details).

6.2 Handling of Non-Serious Adverse Events

All AEs encountered during the clinical study will be reported on the CRF.

- All AEs and SAEs must be recorded on patient’s source documents.
- All AEs and SAEs for patients who receive a treatment assignment code will be recorded in the CRFs. During the active reporting period specified above, all AEs will be reported on the AE page(s) of the CRF. It should be noted that the form for collection of SAE information is not the same as the AE CRF. Where the same data are collected, the forms must be completed in a

consistent manner. For example, the same AE term should be used on both forms. AEs should be reported using concise medical terminology on the CRFs as well as on the form for collection of SAE information.

- Each AE is to be assessed to determine if it meets the criteria for SAEs. If an SAE occurs, expedited reporting will follow local and international regulations, as appropriate.
- Withdrawal due to AE should be distinguished from withdrawal due to insufficient response, according to the definition of AE noted earlier, and recorded on the appropriate AE CRF page.

The information to be entered in the CRF will include:

- The time of onset of any AE or the worsening of a previously observed AE
- The specific type of reaction in standard medical terminology
- The duration of the AE (start and stop dates)

6.2.1 *Severity assessment*

The severity of the adverse event (AE). The severity should be rated as:

- **Mild:** discomfort noted, but no disruption of normal daily activity.
- **Moderate:** discomfort noted of sufficient severity to reduce or adversely affect normal activity.
- **Severe:** incapacitating, with inability to work or perform normal daily activity.

6.2.2 *Causality assessment*

An assessment of the relationship of the adverse event (AE) to the study medication, i.e., according to the definitions below:

Definite: a clinical event, including laboratory test abnormality, occurring in a plausible time relationship to drug administration, and which cannot be explained by concurrent disease or other drugs or chemicals. The event must be pharmacologically or phenomenologically plausible, and its clinical response to withdrawal of the drug (dechallenge) should be clinically plausible. It must also be confirmed by a satisfactory rechallenge procedure.

Probable/likely: a clinical event in which a relationship to the IMP seems probable because of such factors as a clear temporal association with the use of the IMP, lack of alternative explanations for the event or other factors.

Possible: the essential distinctions between ‘Probable’ and ‘Possible’ are that in the latter case there may be another equally likely explanation for the event (could also be explained by disease or other drugs) and/or there is no information or uncertainty with regard to what has happened after stopping.

Unlikely: a clinical event with a temporal relationship to IMP administration that makes a causal relationship improbable and / or in which other factors suggesting an alternative aetiology exist. Such factors include a known relationship of the adverse event to concomitant drug, the patient’s disease state or environmental factors including common infectious diseases.

Conditional/Unclassified: A clinical event, including laboratory test abnormality, reported as an adverse reaction, about which more data are essential for a proper assessment or the additional data are under examination.

Unassessable: A report suggesting an adverse reaction which cannot be judged because information is insufficient or contradictory, and which cannot be supplemented or verified.

Not related: Not suspected to be reasonably related to the IMP. A reasonable alternative explanation must be available.

In addition, if the investigator determines an SAE is associated with study procedures, the investigator must record this causal relationship in the source documents and CRF, as appropriate, and report such an assessment in accordance with the SAE reporting requirements, if applicable.

As far as possible, all investigators should follow-up participants with AEs until the event is resolved or until, in the opinion of the investigator, the event is stabilized or determined to be chronic. Details of AE resolution must be documented in the CRF. Participants should be followed-up for 30 days after receiving the last dose of study medication and any AEs, which occur during this time, should be reported according to the procedures outlined above. Any significant changes in AEs should be reported even though the patient has completed the study, including the protocol-required post-treatment follow-up.

6.3 Serious Adverse Events reporting

All SAEs and follow-up information must be reported to the sponsor on a SAE form within 24 hours of investigator awareness of the event.

All non-serious AE notified at the same time of serious AE shall be recorded and notified to the Pharmacovigilance unit of the sponsor.

The description of SAE will include a description of the AE with sufficient details to allow for a complete medical assessment of the case and independent determination of possible causality. Information on other possible causes of the event, such as concomitant medications and illnesses must be provided. In the case of a patient death, a summary of available autopsy findings must be submitted as soon as possible to Sponsor or its designated representative.

All adverse events encountered during the clinical study must be reported on the CRF as soon as the data are available. Therefore, data will be accessible immediately by the sponsor or designee.

Serious adverse events (SAEs), whether or not associated with study medication administration, will be recorded both on the Adverse Event form of the CRF and the SAE form (available from the CRF web site or from the Investigator's study files).

ALL SAEs occurring during this study and up to 30 days after a patient discontinued or completed the study, whether or not related to the administration of study medications, must be reported by faxing the completed SAE form, after reviewing the report for consistency and accuracy within 24 hours of awareness by the investigator, to:

Pharmacovigilance Department

[contact]

Medical Assistance

If there is a need to discuss any medical issues concerning a serious adverse event or to report a serious adverse event during the business hours, MEDDAY can be contacted at:

[contact]

[contact]

6.4 Sponsor Reporting Requirements to Regulatory Authority

Adverse event reporting, including suspected serious unexpected adverse reactions, will be carried out in accordance with applicable local regulations.

In case of occurrence of SAEs attributable to experimental treatment, the DMSB will be seized by the investigator and / or sponsor to decide on the continuation of the trial.

7 STATISTICAL CONSIDERATIONS

7.1.1 Determination of sample size

This pilot study is exploratory. The various clinical and electrophysiological endpoints will allow defining which of them will be the most relevant in confirmatory randomized controlled trials.

It is assumed that 15 patients is a sufficient sample size for 1) detect an effect of MD1003 in demyelinating peripheral neuropathies, and 2) rank the best endpoints for confirmatory studies in the three most common demyelinating peripheral neuropathies.

7.1.2 Definition of populations for analysis

Safety population

All patients who receive at least one dose of study medication will be included.

Intent-to-treat population (ITT)

All patients who receive at least one dose of study medication and with at least one assessment at baseline and during the study will be included.

All analyses will be according to the intent-to-treat principle (all patients will be analysed).

Per Protocol population (PP)

All patients of the ITT and without major protocol deviations.

7.1.3 General considerations

Descriptive analyses will be performed.

Data will be summarized as follows: Continuous variables by descriptive statistics (number of patients [N], mean, standard deviation, minimum, median and maximum); categorical data by absolute and relative frequencies (n and %). No imputation will be performed on missing data.

The analyses described below are those intended to be performed based on an estimate of the available data. If the applicable data is not available; the analyses will be adapted accordingly.

The analyses described below are those intended to be performed based on an estimate of the available data. If applicable data are not available; the analyses will be adapted using the Last Observation Carried Forward (LOCF) imputation method.

Quality assurance of the data and statistical analysis and the development of the statistical part of the study report will be made by Medday or designee.

All clinical data recorded as verbatim into the CRF will be encoded in MedDRA last version.

All analyses will be conducted on the ITT with a global significance level of 5%.

Primary and secondary endpoints will be considered as exploratory analyses with no defined order of analysis.

7.1.4 Primary efficacy analyses

Principal analysis of the primary efficacy endpoint

The primary endpoint will be evaluated as the change from baseline to week 48 of the following criteria of demyelination:

- Motor nerve conduction velocity,
- Distal latency,
- F wave latency,
- Length of motor nerve potential.

Eight nerves will be assessed for those four criteria. Change will be considered significant when the last value is 10% improved compared to the baseline value for two out of these four parameters in at least three nerves out of eight investigated nerves.

7.1.5 Secondary efficacy analyses

The analysis of the secondary endpoints will be descriptive:

1. Change in the ONLS score;
2. Change in the MRC sum score
3. Change in INCAT sensory Score
4. Change in the posturography score;
5. Changes in the time to 25 feet walk and the 6 minutes walk test;
6. Changes in minimal and maximal duration of the absolute refractory period (in ms), in refractoriness and supernormality (in %), in strength-duration time constant (in ms) and in rheobase (in mA) for the ulnar motor nerve.

The secondary clinical endpoints will be ranked differently according to initial diagnosis:

- CIDP:

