3.2.3 Biotin and primary or secondary progressive multiple sclerosis

Previous human experience in a pilot study and results of two phase IIb/III studies (EudraCT No. 2013-002113-35 and 2013-002112-27, namely MS-SPI study and MS-ON study, respectively) have provided evidences of a favourable benefit/risk balance of MD1003 (biotin 300 mg/day) in adult patients with progressive MS, but not in MS patients with relapsing-remitting MS.

The randomized, double-blinded MS-SPI study included adult patients with PP and SP MS with no evidence of inflammatory activity (n=103 in the MD1003 group and n=54 in the placebo group). Improvement was defined as either a decrease in disability score (EDSS) or an improvement in TW25 (a timed 25-foot walk) as compared to the best EDSS and TW25 scores obtained either at the screening or randomisation visits. Results demonstrated a strong and clinically meaningful benefit of MD1003 compared to placebo with (1) improvement of a significant proportion of patients after 9 months confirmed at 12 months (primary endpoint, p=0.005), (2) stabilized mean EDSS score (p=0.014) and (3) better clinical global impression of change (p<0.0001).

The randomized, double-blinded MS-ON study included adult patients with either visual loss following an optic neuritis relapse (ON relapses, n=62) or chronic progressive optic neuritis (progressive ON, n=31). The primary endpoint was the mean change in 100% contrast visual acuity (VA) at 6 months from baseline of the worst eye. In patients with ON relapses, VA improved in both placebo and MD1003 groups by a mean of 0.06 LogMAR, i.e. 3 letters in both groups, without any superiority of MD1003. In the progressive ON subgroup, VA worsened by a mean of 0.03 LogMAR in the placebo group, while it improved by a mean of 0.06 LogMAR in the MD1003 group. Although the number of patients was too

small to reach statistical significance, these results are in line with the positive results of the MS-SPI trial and indicate that MD1003 should be indicated in progressive MS only.

It is hypothesized that the positive effects of high doses of biotin in progressive MS are linked to:

(1) Increased energy production in demyelinated neurons. This would avoid neurodegeneration and would improve neuronal functioning.

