5.6 Visits schedule and evaluations

5.6.1 Patient follow-up schedule

	Week -4	Week 0	Week 12	Week 24	Week 36	Week 48
	Selection	Inclusion	Follow-up			End
STUDY WINDOWS		+/-5 days	+/-10 days			+/- 15 days
Informed consent	X					
Inclusion criteria	X	X				
Non-inclusion criteria	X	X				
Medical history	X					
Clinical examination	X	X	X	X	X	X
Neurophysiological examination		X		X		X
MRC sum score		X	X	X	X	X
INCAT sensory Score		X	X	X	X	X
Posturography score		X		X		X
ONLS score		X	X	X	X	X
Timed 10-meter walk test		X	X	X	X	X
6-min walk test		X	X	X	X	X
Excitability testing		X		X		X
AEs reporting		X	X	X	X	X
Concomitant therapies	X	X	X	X	X	X
Biological test ¹	X ²					X
Serum sample	X			X		X
Study drug dispensation		X	X	X	X	
Compliance check			X	X	X	X

¹ Biological safety panel includes: RBC, hemoglobin, mean corpuscular volume, WBC, platelets, electrolytes (Na, K, HCO₃, Ca), protein, creatinine, glomerular filtration rate, fasting blood glucose, AST, ALT, total and free bilirubin, gamma glutamyl transferase, alkaline phosphatase, triglyceride, cholesterol, PT, aPTT, INR

² Biological aetiology additional panel: Serum protein electrophoresis, IgA measurement, HbA1c, HBsAg, HIV, HCV tests, fibrinogen

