Appendix

Timed 10-meter walking test:

- The patient should be instructed to walk without assistance 10 meters (32.8 feet) and the time is measured for the intermediate 6 meters (19.7 feet) to allow for acceleration and deceleration
 - start timing when the toes of the leading foot crosses the 2-meter mark
 - stop timing when the toes of the leading foot crosses the 8-meter mark
 - assistive devices can be used but should be kept consistent and documented from test to test
- If physical assistance is required to walk, this should not be performed
- The test can be performed at preferred walking speed or fastest speed possible
- The documentation should include the speed tested (preferred vs. fast)
- Three trials have to be performed and the average of the three trials calculated

Set-up (derived from the reference articles):

- measure and mark a 10-meter walkway
- add a mark at 2-meters
- add a mark at 8-meters

Patient Instructions (derived from the reference articles):

Maximum speed trial: “I will say ready, set, go. When I say go, walk as fast as you safely can until I say stop”

Instruction in French: « Je vais vous dire attention, prêt, partez. Lorsque je dis partez, marchez prudemment aussi vite que vous pouvez jusqu'à ce que je vous dise stop. »

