2.2 Changes to the conduct of the analysis

The name of "ITT population" has been replaced by "FAS population" to be compliant with the ICH guidelines.

As sensitivity analysis of the efficacy endpoints, a Wilcoxon signed rank test will be performed to assess if the changes from baseline at week 48 in the efficacy criteria are statistically significant considering an alpha level of 5%.

Regarding secondary efficacy criteria, missing data at week 48 will be imputed considering LOCF approach.

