10.2 Secondary criteria

The secondary endpoints are changes from baseline to week 48 in:

- ONLS score,
- MRC subscore (total muscle) and total score,
- INCAT Sensory Sum (ISS) Score,
- Posturography parameters:
 - o Analysis of Walking: all parameters in the condition spontaneous speed
 - o Analysis of Balance: center of pressure on anterior/posterior axis and center of pressure covered area in the four conditions (Open/Closed eyes and Spread Feet (60s)/Feet together (60s))
- Timed 10-meter walk test (s) (whatever the assistance),
- Distance 6-min walk test (m) (whatever the assistance),
- Supernormality (%),
- Strength-duration time constant (ms),
- Rheobase (mA),
- Refractoriness (%),
- Minimal absolute refractory period (ms),
- Maximal absolute refractory period (ms).

ONLS score, MRC score, INCAT Sensory Sum score, timed 10-meter walk test and distance 6-min walk test will be described at baseline and each post-baseline visit by disease group and overall on the FAS population. The absolute changes from baseline will be provided at week 48.

Posturography parameters and excitability testing (Supernormality, Strength-duration time constant, Rheobase, Refractoriness, Minimum and maximum absolute refractory period) will be described at baseline, week 24 and week 48 by disease group and overall on the FAS population. The absolute changes from baseline to week 48 will be also produced. Regarding the posturography parameters of the analysis of balance, the absolute changes from baseline to week 48 will be also produced only if ‘orthostatic position, bare foot on a force platform’ is reported and not when the test was conducted in a different condition specified under “other”. A Wilcoxon signed rank test will be performed overall for each secondary criterion to assess if the absolute change from baseline is statistically significant at week 48.

In addition, a boxplot will be provided for each parameter displaying Q1, median and Q3 values at each visit by disease group.

Absolute change from baseline will be calculated as (value at week 48 – value at baseline).

Listings of secondary criteria will be provided.

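### Carrying the last walk time forward to week 48 hides patients who lose the timed walk during the study

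*Protocol*

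**What the plan says.** **Which walk.** The schedule in Protocol 5.6.1 has the "Timed 10-meter walk test" at weeks 0, 12, 24, 36 and 48. Protocol 5.7.1.7 has the patient walk 10 m, and "Only the middle 6 m, however, is timed to eliminate the effects of acceleration and deceleration". Only item 5 of Protocol 7.1.5 differs, with "Changes in the time to 25 feet walk and the 6 minutes walk test". The one other 25-foot walk in the documents is an outcome of the earlier progressive-MS study (Protocol 3.2.3: "an improvement in TW25 (a timed 25-foot walk").

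**Who has a value.** Protocol 5.3.2 excludes patients who cannot perform the 10-meter walk. The appendix on the test has it done without assistance, allows assistive devices, and adds: "If physical assistance is required to walk, this should not be performed". SAP 10.2 defines the variable as "Timed 10-meter walk test (s) (whatever the assistance").

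**What happens to a missing value.** For the secondary criteria, SAP 2.2 says that "missing data at week 48 will be imputed considering LOCF approach", and SAP 3.2 repeats this. Neither document has a separate rule for a patient who could not do the test.

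**How it is analysed.** SAP 10.2 describes the absolute change to week 48 in seconds and tests it with a Wilcoxon signed-rank test on all patients pooled, two-sided at 5% (SAP 3.1).

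**The concern.** Because inability to walk is an exclusion at entry, a test that cannot be done at week 48 because of the neuropathy marks a loss during the study. That is the worst result this endpoint can show. Carry-forward replaces it with a time recorded while the patient could still walk, so the patient may look nearly unchanged, or even improved. The error has one direction: it favours no worsening.

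The endpoint is exploratory, but it matters for what the study is meant to deliver. The timed walk is ranked second among the clinical endpoints in CIDP and third in anti-MAG and CMT (Protocol 7.1.5). The study is to identify the best endpoints (Protocol 7.1.1) and to supply the assumptions for the sample size of a placebo-controlled trial (Protocol 4). A walk test that cannot register loss of walking would be judged on incomplete evidence.

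**Working it through.** **1. The plan's own distances.** With 1 ft = 0.3048 m, 10 m is 10/0.3048 = 32.8 ft and 6 m is 6/0.3048 = 19.7 ft. Both match the appendix, and the 2-m and 8-m marks give 8 − 2 = 6 m timed. A 25-foot walk is 25 × 0.3048 = 7.62 m, which is neither the distance walked nor the distance timed.

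**2. Does the label affect the analysis?** Multiplying every time by a constant changes no sign or rank. In simulated data for 15 patients the signed-rank p-value was 0.0479 for the change in seconds and 0.0479 for that change times 10/6.

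**3. The path of a patient who loses the test.** Able at entry (Protocol 5.3.2); physical assistance needed later; test not performed (appendix); week-48 value missing; earlier time carried forward (SAP 2.2, 3.2); change computed and ranked (SAP 10.2). No step records the loss.

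One detail is open. SAP 3.2 restricts carry-forward to post-baseline values for the primary criteria but does not say so for the secondary ones. A patient who loses the test before week 12 would get either a baseline value, hence zero change, or no value. A standard signed-rank test discards zero differences, so either way the loss drops out.

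**4. Possible size.** Inputs: n = 15 (SAP 1.3); two-sided 5% (SAP 3.1). Assumption: k = 0 to 2 patients lose the test, since the documents give no rate. W is the sum of the ranks of the patients who worsen, and

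p = 2 × (number of subsets of ranks 1 to 15 with sum ≤ W) / 2^15, where 2^15 = 32,768.

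Scenario A: all other patients improve. Under carry-forward the k carried values are taken as the smallest changes and as worsenings; under worst rank they take the top ranks.

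| k | Carry-forward | Worst rank |
|---|---|---|
| 1 | W = 1; 2 × 2/32,768 = 0.0001 | W = 15; 2 × 137/32,768 = 0.008 |
| 2 | W = 1 + 2 = 3; 2 × 5/32,768 = 0.0003 | W = 14 + 15 = 29; 2 × 1,364/32,768 = 0.083 |

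If the k patients are simply dropped, p = 2/2^14 = 0.0001 for k = 1 and 2/2^13 = 0.0002 for k = 2, as favourable as carry-forward.

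Scenario B: two of the patients still walking also worsen, at ranks 4 and 7 among those walkers, and the carried values are small gains.

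| k | Carry-forward | Worst rank |
|---|---|---|
| 1 | W = 5 + 8 = 13; p = 0.005 | W = 4 + 7 + 15 = 26; p = 0.055 |
| 2 | W = 6 + 9 = 15; p = 0.008 | W = 4 + 7 + 14 + 15 = 40; p = 0.28 |

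With k = 0 the two rules agree. They also agree if the carried times are already the largest worsenings in the sample. The tables show what the rule can do, not what it will do.

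**The case against.** **Loss of walking is visible elsewhere.** ONLS leg grades 5 to 7 record wheelchair use, and ONLS is ranked first in every disease group. This is true, and it limits the harm to the overall reading of the trial. It does not correct the timed walk, which has its own table, boxplot and test.

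**The carried value may already show decline.** The walk is also measured at weeks 12, 24 and 36. This can shrink the error. It removes it only if the last time is already as bad as any in the sample.

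**Assisted walks may have a time.** SAP 10.2 accepts times whatever the assistance, so a patient needing physical help might not be missing. That conflicts with the appendix, and a patient who cannot walk even with help would still have no time.

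**The data review meeting could deal with it.** SAP 3.2 provides for a discussion of missing secondary data, but then states the outcome: carry-forward at week 48.

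**Readings that go too far.** A reader might infer that the reported seconds misstate walking speed, by 10/6 (+67%) if taken as a 10-m time or 7.62/6 (+27%) if taken as a 25-foot time. The documents do not support this. The SAP derives no speed from this test, the protocol defines the timed distance consistently, and step 2 shows that the label alters no result. Nor does the 25-foot wording alter the analysis: Protocol 7.1.5 itself names the 10-meter walk in all three rankings, and the SAP has no 25-foot variable.

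A reader might also infer that seconds must be replaced by speed because one slow walker inflates the SD. In a simulation with assumed baseline speed 1.0 m/s (SD 0.2) and 8% visit-to-visit variation, one patient slowing to 0.2 m/s raised the SD of change about 12-fold in seconds (0.505 to 6.14 s) and 2.8-fold in speed (0.080 to 0.222 m/s). At 0.5 m/s the ratios were only 3.0 and 1.9. The SAP uses a rank test and reports medians and quartiles, Protocol 5.7.1.7 makes speed optional, and SAP Table 14.4.2.7 already gives a gait speed. The choice of scale is a preference.

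**Conclusion.** The concern holds for the missing-data rule. Followed as written, the SAP scores a patient who loses the timed walk with an earlier time from when they could walk, and so biases the change and its test toward no worsening. The conclusion about direction rests on Protocol 5.3.2, the appendix and SAP 2.2 and 3.2 alone.

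The size rests on assumptions: none of 15 patients losing the test means no effect. If all others improve, one such patient leaves both rules below 5% (0.0001 and 0.008), while two separate them (0.0003 and 0.083). If two other patients also worsen as in scenario B, one is enough (0.005 and 0.055).

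The endpoint is secondary and exploratory, so this is a correction that should be made but does not threaten the primary result. The 25-foot name and the unlabelled 6 m are wording corrections only.

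**What to change.** In SAP 3.2 and 10.2:

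- Limit carry-forward to walk tests missed for reasons other than inability, and state whether a baseline value may be carried.
- When the timed walk could not be done because of the neuropathy, give the patient the worst rank (the largest worsening) in the signed-rank test.
- For the 6-minute walk, enter 0 m if the patient cannot walk, with the same worst-rank rule in the test.
- Report the number of patients unable to do each test beside the summaries.

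A score of zero alone is not enough. On absolute change in speed, a patient going from 0.5 to 0 m/s (−0.5) would rank better than one going from 1.0 to 0.2 m/s (−0.8). The worst rank must be assigned explicitly.

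Reconcile SAP 10.2 on assistance with the appendix, so that it is clear which assisted walks yield a time.

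Wording: change the 25-foot walk in Protocol 7.1.5 to the 10-meter walk, and label Table 14.4.2.5 and Figure 14.4.3.5 as time over the middle 6 m. Speed (6 m divided by the mean time of the three trials) may be added descriptively.

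Cost: a short SAP change, which Protocol 7.1.9 allows as a complementary SAP if the plan is already final, plus relabelling. The reason for each missing walk must be taken from the CRF or source documents.
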